### **3.2. Study Treatment**

All participants must be dosed within 10 hours of time of trauma/last known normal (LKN) and within 6 hours of hospital arrival. Dosing should be initiated within 1 hour of randomization and continue for 96 hours (4 days). Participants will receive study treatment (3 mg/day or 5 mg/day) or matching placebo administered as a 3-stage continuous infusion: a bolus IV dose (given over 2 minutes), followed by 2 different infusion rates (a rapid IV infusion for 6 hours followed by a slow IV infusion for the remaining 90 hours) for 96 hours total. Participants will be randomly assigned to 3 mg/day study treatment, 5 mg/day study treatment, 3 mg/day matching placebo, or 5 mg/day matching placebo in a 1:1:1:1 ratio, stratified based on baseline contusion volume per Investigator assessment of noncontrast computed tomography scan or site local radiologic assessment (3 to 10 mL or > 10 mL), baseline GCS (5 to 8, 9 to 12, or 13 to 15), age ( $\leq$  70 years old or > 70 years old), and region (North America [United States] or Rest of World).

By-treatment-group analysis will be displayed as:

- Placebo
- BIIB093 3 mg/day

- BIIB093 5 mg/day
- BIIB093 combined
- Total, if applicable

The treatment groups are defined as follows.

### **3.2.1 Randomized Treatment Group**

Randomized treatment refers to the treatment assigned to a participant at the initial randomization.

Accrual, study conduct, participant disposition, demographics, baseline disease characteristics, physical measurements, concomitant medications and non-drug therapies, efficacy and outcome research results will be analyzed and presented by randomized treatment group, unless otherwise specified.

### **3.2.2 Actual Treatment Group**

Actual treatment refers to the actual study drug received by a participant.

- Randomized participants who are dosed but never receive any BIIB093 during study treatment administration will be assigned to placebo group.
- Randomized participants who receive any BIIB093 will be assigned to BIIB093 3 mg/day group, if the IV dose during bolus  $< 0.17$  mg and the following IV infusion received by the participant  $< 11.31$  mg for Infusion 1 and  $< 13.525$  mg for Infusion 2; refer to Table 1 of the protocol.
- Randomized participants who receive any BIIB093 will be assigned to BIIB093 5 mg/day group, if the IV dose during bolus  $\geq 0.17$  mg or the following IV infusion received by the participant  $\geq 11.31$  mg for Infusion 1 or  $\geq 13.525$  mg for Infusion 2.
- Randomized participants who never receive any study drug (neither BIIB093 nor the matching placebo) will have missing actual treatment group and will be excluded in the analysis by actual treatment group.

Study results for safety (adverse events, serious adverse events, laboratory, vital signs, liver function test, electrocardiogram [ECG]), extent of exposure, [REDACTED] will be analyzed and presented by actual treatment group.

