4.5. Dosing Rationale

4.5.1. Dosing Regimen

Dosing must be started within 10 hours of trauma/last known normal (LKN) and within 6 hours of arrival to the hospital. Dosing should be initiated within 1 hour of randomization, and continue for 96 hours (4 days). The dosing duration of 96 hours (4 days), spans the period during which patients are thought to be at highest risk for contusion expansion. Two BIIB093 dose levels will be administered (Table 1).

Table 1: BIIB093 Dosing Regimen

	IV bolus (slow IV push via syringe)	Infusion 1	Infusion 2
3 mg/day	0.13 mg (over approximately 2 minutes)	0.99 mg (0.1644 mg/h for 6 h)	10.21 mg (0.1134 mg/h for 90 h)
	Total dose: Day 1 (3.16 mg), Day 2 (2.72 mg), Day 3 (2.72 mg), Day 4 (2.72 mg) = 11.3 mg		
5 mg/day	0.21 mg (over approximately 2 minutes)	1.63 mg (0.2722 mg/h for 6 h)	16.84 mg (0.1871 mg/h for 90 h)
	Total dose: Day 1 (5.21 mg), Day 2 (4.49 mg), Day 3 (4.49 mg), Day 4 (4.49 mg) = 18.7 mg		

h = hour(s); IV = intravenous.

Note: 3 mg/day and 5 mg/day are approximate total daily doses.

Refer to the Directions for Handling and Administration (DHA) for corresponding mL/h rates and further information on windows for infusion timings.

The 2 BIIB093 dose levels (3 mg/day and 5 mg/day) selected for this study were determined based on clinical safety and pharmacokinetic (PK) data and preliminary exposure-response (efficacy/safety) analyses from the Phase 1 healthy volunteer studies (Study 101 and Study 102) and the Phase 2 LHI studies (Study 201 and Study 203).

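### SAP 3.2.2 prints the Infusion 1 cut-off for actual treatment group as 11.31 mg, about seven times the largest planned Infusion 1 dose; 1.31 mg appears to be intended

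*SAP*

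**What the plan says.** SAP 3.2.2 defines the actual treatment group from the drug received. A participant given any BIIB093 goes to 3 mg/day if the bolus, Infusion 1 and Infusion 2 amounts are all below their cut-offs, and to 5 mg/day if any one of them is reached. The cut-offs are 0.17 mg (bolus), 11.31 mg (Infusion 1) and 13.525 mg (Infusion 2). The Infusion 1 figure appears in both rules: "11.31$ mg for Infusion 1 and" for 3 mg/day and "11.31$ mg for Infusion 1 or" for 5 mg/day. (The dollar sign is left over from text conversion.) For the source of the doses, the 3 mg/day rule tells the reader to "refer to Table 1 of the protocol".

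Protocol 4.5.1, Table 1, gives:

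- Infusion 1: "0.99 mg (0.1644 mg/h for 6 h" at 3 mg/day and "1.63 mg (0.2722 mg/h for 6 h" at 5 mg/day.
- Infusion 2: "10.21 mg (0.1134 mg/h for 90 h" at 3 mg/day and "16.84 mg (0.1871 mg/h for 90 h" at 5 mg/day.
- Bolus: 0.13 mg and 0.21 mg.

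SAP 3.2.2 states that safety and exposure results "will be analyzed and presented by actual treatment group". SAP 3.2 displays 3 mg/day and 5 mg/day as separate groups. The SAP version history gives correction of this derivation for the 5 mg/day group as the reason for version 2.0.

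**The concern.** A cut-off meant to separate 0.99 mg from 1.63 mg has to lie between them. At 11.31 mg, every participant dosed near the protocol amounts falls below it, so one of the three criteria does nothing. The classification then rests on the bolus and Infusion 2 alone.

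This matters where those two fail to identify a 5 mg/day participant and Infusion 1 would have done so. That participant is counted under 3 mg/day in the by-dose safety and exposure columns, which carry the dose-safety comparison in this two-dose study. A low Infusion 2 total can result from a rate reduction for hypoglycemia (Protocol 11.2, Table 4), so any mislabelling need not be unrelated to the main safety signal.

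**Working it through.** **1. Table 1 amounts from rate × time.** Infusion 1: 0.1644 × 6 = 0.986 mg and 0.2722 × 6 = 1.633 mg. Infusion 2: 0.1134 × 90 = 10.206 mg and 0.1871 × 90 = 16.839 mg. Table 1 is internally consistent.

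**2. How the cut-offs were set.** Midpoint of the two Table 1 doses against the SAP figure:

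| Stage | Midpoint (mg) | SAP (mg) |
|---|---|---|
| Bolus | (0.13 + 0.21)/2 = 0.17 | 0.17 |
| Infusion 1 | (0.99 + 1.63)/2 = 1.31 | 11.31 |
| Infusion 2 | (10.21 + 16.84)/2 = 13.525 | 13.525 |

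Two agree exactly and one does not. Other constructions also fail to give 11.31: geometric mean of the Infusion 1 doses, 1.27; midpoint of bolus plus Infusion 1, 1.48; Infusions 1 and 2 together at 3 mg/day, 11.20; total dose at 3 mg/day, 11.33; midpoint of Infusions 1 and 2 together, 14.835; midpoint of the total doses, 15.005.

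**3. Can 11.31 mg be reached?** 11.31/1.633 = 6.9 times the largest planned Infusion 1 amount. At 0.2722 mg/h it would take 11.31/0.2722 = 41.6 h, against 6 h planned.

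**4. When the label differs.** Because the 5 mg/day criteria are joined by *or*, the printed rule and a 1.31 mg rule disagree only if bolus < 0.17 mg, Infusion 2 < 13.525 mg and Infusion 1 ≥ 1.31 mg.

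- Bolus condition for a 5 mg/day participant: a shortfall of more than (0.21 − 0.17)/0.21 = 19%.
- Infusion 2 condition, infusion stopped: before Hour 6 + 13.525/0.1871 = 78.3.
- Infusion 2 condition, rate reduced to 0.0795 mg/h and kept there: before Hour 6 + (13.525 − 0.0795 × 90)/(0.1871 − 0.0795) = 65.2.
- Infusion 2 condition, rate reduced and at once uptitrated to 0.1134 mg/h: before Hour 6 + (13.525 − 0.1134 × 90)/(0.1871 − 0.1134) = 51.0.

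**5. Worked labels, 5 mg/day arm, full Infusion 1 (1.633 mg).** These are illustrative records, not data.

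| Bolus (mg) | Infusion 2 (mg) | As printed | With 1.31 |
|---|---|---|---|
| 0.15 | 54 × 0.1871 = 10.10 (stop at Hour 60) | 3 mg/day | 5 mg/day |
| 0.15 | 34 × 0.1871 + 56 × 0.0795 = 10.81 (reduced at Hour 40 and kept) | 3 mg/day | 5 mg/day |
| 0.21 | 10.10 (stop at Hour 60) | 5 mg/day | 5 mg/day |
| 0.15 | 84 × 0.1871 = 15.72 (stop at Hour 90) | 5 mg/day | 5 mg/day |

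**6. Size per participant.** With 40 planned per active dose, moving one participant changes a percentage by at most 1/40 = 2.5 points in the column left and 1/41 = 2.4 points in the column joined, whatever the event count.

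**The case against.** The strongest answer is that the consequence is remote. The bolus is given first, by syringe over about 2 minutes, and Protocol Table 4 changes infusion rates only. No planned dose modification produces a short bolus, and a recorded bolus of 0.17 mg or more settles the label alone. SAP 5.5.1 also counts re-boluses in exposure; if they count towards the bolus amount in 3.2.2, which the SAP does not say, a bolus total below 0.17 mg is rarer still. All of this stands and keeps the point minor, but it does not make the printed criterion work.

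The 2.5-point bound belongs to columns of 40. At an interim look with about 90 dosed, an active arm would hold about 90/4 = 22 or 23 participants, and one relabelling could move a percentage by up to 1/22 = 4.5 points. That qualification is right.

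The SAP never states a midpoint rule, so 1.31 is an inference, and the reviewed text was extracted from PDF. Both points are fair and are reasons to check the source. But the same figure appears in both rules, the neighbouring cut-offs are intact, and the failure of 11.31 does not depend on what was intended.

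**Conclusion.** The Infusion 1 cut-off is wrong as written. At protocol doses it is never reached, and 1.31 mg is the evident intended value. The error is minor. Only participants meeting all three conditions in step 4 are affected, and the documents give no rate of short boluses from which to count them. The same conditions would also cover a 3 mg/day participant who, by deviation, received at least 1.31 mg in Infusion 1; there too the criterion is silent.

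The reach is the split between 3 and 5 mg/day in safety, exposure and any other output by actual treatment group. SAP 3.6.2 analyses the per-protocol set by actual treatment but states no dose split there, so by-dose per-protocol results are affected only if produced. The primary analysis uses randomized groups, and the main efficacy comparisons in SAP 5.6.1 set BIIB093 combined against placebo. Neither these nor the placebo and combined columns change. The conclusion assumes that the extracted figure matches the source SAP.

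**What to change.** Check the source SAP against Protocol Table 1, have the sponsor confirm the intended value, and replace 11.31 mg with 1.31 mg in both rules of SAP 3.2.2. Check that the derivation program uses the corrected figure. Do this before the Day 4 database lock, and before any interim output by actual treatment group. The cost is one number in two places and a program check. This is an analysis threshold and touches no dose.

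Optionally, add one sentence on the limit that remains. A 5 mg/day participant with a short bolus and a low Infusion 2 total, whose Infusion 1 total is itself below 1.31 mg because of a stop or a Table 4 reduction, is still labelled 3 mg/day. For example, 3.5 h at 0.2722, 0.5 h at 0.1644 and 2 h at 0.0795 mg/h give 0.953 + 0.082 + 0.159 = 1.194 mg.

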## **3.3. Study Periods**

### **Pretreatment Period**

The pretreatment period begins at the admission to hospital at the screening visit until start time of study drug infusion (Hour 0).

Measurements taken before the time of study drug infusion at Hour 0 are considered pretreatment for all data domains. If the time of measurement is missing, measurements taken on

Day 1 are considered pretreatment for the following data domains: demography, disease history, ECG, human genotyping, laboratory test results, medical history, physical examinations, participant status, and vital signs.

Baseline value is defined as the last non-missing value before the time of study drug infusion (Hour 0) or prior to or on Day 1 if the time of study drug infusion is missing.

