11.4.1.1. Allowed Concomitant Therapy

11.4.1.1.1. Interventions Related to Blood Glucose

In a joint statement from the American Diabetes Association and the European Association for the Study of Diabetes, the International Hypoglycemia Study Group concluded that a BG level of < 54 mg/dL (~ 3.0 mmol/L) alone, without symptoms, is clinically important and should be included in reports of clinical studies involving glucose-lowering drugs [International Hypoglycaemia Study Group 2017]. The statement further recommends an “alert” level of 70 mg/dL (~ 3.9 mmol/L) for BG. The following interventions are designed in accordance with those recommendations; however, Investigators must use their own medical judgment in conjunction with referencing the guidance (Table 5).

Insulin

Insulin and other BG-lowering agents are not permitted during study treatment administration when BG < 140 mg/dL (~ 7.8 mmol/L).

Nutrition

Enteral nutrition is encouraged to be initiated within 24 hours of admission if consistent with SOC. Participants may need postpyloric administration of nutritional support.

Maintenance Dextrose-Containing IV Solution

During the study treatment infusion period, BG monitoring is required as follows:

- Hour 0 to Hour 24, monitor hourly (± 30 minutes)
- Hour 25 to Hour 48, monitor every 2 hours (± 30 minutes)
- Hour 49 to Hour 96, monitor every 4 hours (± 60 minutes)

See Section 5 for further details on timings of BG measurements. If treatment for hypoglycemia is initiated (for BG < 70 mg/dL [~ 3.9 mmol/L]), then BG monitoring is required every 15 minutes (± 10 minutes) until BG is ≥ 80 mg/dL (~ 4.4 mmol/L) for 3 consecutive readings without exogenous bolus glucose supplementation. BG monitoring may be performed more often at the discretion of the Investigator. Table 5 shows how BG should be monitored and managed according to inpatient BG levels.

Total fluid volume, inclusive of study treatment volume, infusion rate, infusion duration, sodium content, and percent of dextrose, should be guided by the clinical status of the subject and medical judgment.

CONFIDENTIAL

The information contained herein may not be used, disclosed, or published without the written consent of Biogen MA Inc.

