### 3. Definitions

#### 3.1. Dates and Points of Reference

The first date of starting study drug infusion (BIIB093 3 mg/day, 5 mg/day or the matching placebo) is referred to as study Day 1. For all the dates in the study

- If a date is on or after study Day 1  
Study Day = (date of interest) – (study Day 1) + 1
- If a date is before study Day 1  
Study Day = (date of interest) – (study Day 1)

Study Hour 0 is defined as the start time of the study drug infusion. For all the times in the study before and during the study drug infusion

- Study Hour = (hour of interest) – (study Hour 0)

For efficacy data that are summarized or analyzed by visit, data collected on all scheduled visits and all unscheduled visits will be mapped to an appropriate analysis visit using the windowing scheme shown in [Table 1](#). If there are 2 or more assessments available in the same analysis window for a subject, unless otherwise specified, the assessment that is closest to the target visit day/time will be used for analysis. If there are 2 or more assessments in the same analysis window with the same distance from the target visit day, the later assessment will be used.

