### **On-Treatment Period**

The on-treatment period begins at the time of study drug infusion (Hour 0) on Day 1 and ends 72 hours after the end of study drug infusion. The window of 72 hours is based on the half-life of study drug and allows the remaining study drug to clear from the participant's system.

Measurements taken after the time of the initiation of study drug infusion (Hour 0) on Day 1 through the end of study drug infusion plus 72 hours are considered on treatment for all data domains. In addition, if the time of measurement is missing, measurements taken on Day 1 are considered on-treatment for the following data domains: AEs, drug dispensation, exposure, non-study medications.

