### Analysis of Blood Glucose

The blood glucose from local laboratory are collected at screening, Hours 0-12, Hour 24, Hour 48, Hour 72, Hour 96 and Day 7 with the normal ranges. Additionally, the Point-of-Care (POC) blood glucose is collected pre-dose, hourly up to Hour 96 without normal ranges. The normal range for POC blood glucose data are assigned as between 70 mg/dL and 139 mg/dL, according to the reference range recommended by the American Diabetes Association for random blood glucose measurements. For all analyses, the two sources of data (local laboratory and POC) will be combined and analyzed together.

Summary of lowest post-baseline value of blood glucose will be provided. The number (%) of participants with post-baseline blood glucose abnormalities ( $<55$  mg/dL,  $<80$  mg/dL,  $<120$  mg/dL) will be summarized by actual treatment group. Blood glucose values for participants with post-baseline blood glucose  $<55$  mg/dL will be listed.

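### Untimed Day 1 ECG, laboratory and vital-sign records default to pretreatment even when labelled post-dose, so on-drug values can drop out of the laboratory and ECG safety tables (minor)

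*SAP*

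**What the plan says.** SAP 3.1 fixes study Day 1 as "The first date of starting study drug infusion". It is a calendar date, so it holds records from both sides of Hour 0.

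SAP 3.3, Pretreatment Period, sorts timed records by Hour 0. When the time is missing, measurements taken on "Day 1 are considered pretreatment for the following data domains: demography, disease history, ECG, human genotyping, laboratory test results", and the list ends with "laboratory test results, medical history, physical examinations, participant status, and vital signs". On baseline the section says "Baseline value is defined as the last non-missing value before the time of study drug infusion (Hour 0", with a fallback to Day 1 or earlier if the infusion time itself is missing.

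SAP 3.3, On-Treatment Period, takes the opposite default elsewhere: if the time is missing, "measurements taken on Day 1 are considered on-treatment for the following data domains: AEs, drug dispensation, exposure, non-study medications".

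The measurements that land on Day 1 are scheduled as follows:
- Glucose, Protocol 11.4.1.1.1: "Hour 0 to Hour 24, monitor hourly".
- ECG, Protocol Table 3: one standard-of-care ECG at Screening, then Minute 5 and Hour 6, with Hour 24 as the next.
- Vital signs, Protocol Table 2: Screening and Hours 0-12.

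SAP 5.7.4 analyses glucose as a laboratory result, pooling local-laboratory and point-of-care values. It reports the lowest post-baseline value and "The number (%) of participants with post-baseline blood glucose abnormalities", with cut-offs of 55, 80 and 120 mg/dL.

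**The concern.** Sending untimed Day 1 laboratory and ECG records to pretreatment suits a trial that takes its Day 1 samples before dosing. In this trial, Day 1 also contains the bolus, the rapid infusion and a dense set of post-dose glucose and ECG measurements. The rule ignores a post-dose label even where one exists.

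Take a participant dosed at 12:00 with a screening glucose of 140 mg/dL at 10:00, and a glucose of 50 mg/dL labelled Hours 0-12 with no clock time. SAP 3.3 makes the 50 a pretreatment value. That record no longer contributes to the lowest post-baseline glucose or to any of the three threshold counts.

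Hypoglycemia is the only adverse drug reaction identified so far (Protocol 4.3.3). If times go missing equally often in all arms, on-drug lows lost in this way would be expected mainly in the active arms, and the laboratory tables would understate the known risk.

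**Working it through.** The plan states no figure that depends on this rule, so there is nothing to reproduce. Two checks were made: how Day 1 records divide around Hour 0, and which analyses a misplaced record would leave.

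**Division of scheduled Day 1 records.** The documents give no distribution of start times. Assumptions: starts are uniform over 24 hours (evaluated every 15 minutes), and the screening glucose and ECG fall on the same date as the infusion start. If screening fell on the previous date, the post-dose share on Day 1 would be higher.

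*Glucose.* For a start within clock hour h (0 to 23), 23 − h hourly post-dose readings remain on Day 1: 23 for a start at 00:00, 11 at 12:00, 5 at 18:00, 1 at 22:00 and 0 at 23:00. The mean of 0 to 23 is 11.5.
- One pre-dose reading: 11.5 / (11.5 + 1) = 0.92.
- Two (an Hour 0 reading also counted as pre-dose): 11.5 / 13.5 = 0.85.
- Three: 11.5 / 14.5 = 0.79.

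Post-dose readings outnumber pre-dose ones for starts before 22:00 with one pre-dose reading (22/24 = 92% of start times), and before 21:00 with two (21/24 = 88%).

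*ECG.* Minute 5 falls on Day 1 for every start time on the grid. Hour 6 does so for starts before 18:00 (18/24 = 0.75). The mean post-dose count is 1 + 0.75 = 1.75, and the share is 1.75 / (1.75 + 1) = 0.64. From 18:00 onward the split is 1 to 1.

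*Vital signs.* About one Screening record against one Hours 0-12 record.

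*Hematology and other chemistry.* Screening is essentially the only scheduled Day 1 sample, so the present rule is reasonable there.

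**From share to error.** These shares equal the chance that an untimed record is misclassified only if times are missing at random. Suppose a pre-dose record is r times as likely to lack a time as a post-dose one. With one pre-dose record, the post-dose share among untimed records is then 11.5 / (11.5 + r) for glucose and 1.75 / (1.75 + r) for ECG. The default is wrong more often than right while r is below 11.5 for glucose (11.5 / 2 = 5.75 with two pre-dose readings) and below 1.75 for ECG. The glucose conclusion is robust to a good deal of imbalance, but the ECG conclusion is not.

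**Analyses affected by one misplaced on-drug record.**
- Lowest post-baseline glucose and the three threshold counts (SAP 5.7.4): the record is not used.
- Shift tables (SAP 5.7.4): the record is not used. If it became baseline and was low, the participant would also leave the at-risk set for shift to low, so later lows would be lost there too.
- Potentially clinically significant glucose (SAP Table 4, low at 2.2 mmol/L or less): the record is not used, and the participant leaves the set if that value is baseline and meets the criterion. The 50 mg/dL example would not meet it, because the protocol equates 55 mg/dL with about 3.1 mmol/L and 2.2 / 3.1 × 55 is about 39 mg/dL.
- ECG by-visit summaries (SAP 5.7.5): an untimed Minute 5 or Hour 6 record leaves the post-dose windows. Because the worst record in a window is shown, it could be displayed as the pretreatment value.
- Adverse events (SAP 3.3 and 5.1.2): an untimed event on the start date is on-treatment, and treatment-emergent unless its stop is shown to precede dosing. The same episode can therefore be an on-treatment event and a pretreatment laboratory value.

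**The case against.** A reader might infer that a Day 1 hypoglycemia could vanish from the safety report. The documents do not support that. Confirmed glucose below 55 mg/dL is an event of special interest, upgraded to a serious adverse event (Protocol 15.3.2), and SAP 5.7.2 plans summaries and listings of such events. A reading below 70 mg/dL must be repeated (Protocol 14.3), and once treatment starts, readings follow every 15 minutes. The threshold summary counts participants, so one timed repeat below 55 mg/dL keeps the participant in that count.

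A reader might also take 92% and 64% as error probabilities. Missing times may well be concentrated before dosing: baseline data may come from existing medical records (Protocol 9.1) and the predose ECG has no time window, whereas post-dose ECGs and glucose readings have windows that cannot be checked without clock times.

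A third inference is that baseline will be contaminated. The SAP does not say how an untimed record ranks against a timed pre-dose one, so this is possible but not established. A baseline of 50 mg/dL would also conflict with exclusion criterion 21 and should prompt a query. The fallback for a missing infusion time should rarely apply, since Protocol 11.1 requires start and end times for each bag.

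Finally, the glucose and QTc discontinuation criteria in Protocol 10.1 are applied at the bedside, and no SAP classification alters them.

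All of this stands and limits the consequence. It does not cure the rule: a record labelled Hour 6 is still classed as pretreatment. The adverse-event route does not replace the counts below 80 and 120 mg/dL, the lowest value, the shift tables or the ECG summaries.

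**Conclusion.** The rule is wrong as written for glucose and ECG, and unsafe for vital signs, because it overrides a post-dose label on a day when most scheduled glucose and ECG records are post-dose, late starts excepted. The split rests on uniform start times and same-day screening.

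The effect is confined to descriptive laboratory, vital-sign and ECG safety tables, to a possible but unproven effect on baseline, and to possible disagreement between those tables and the adverse-event tables. No efficacy analysis or hypothesis test depends on it. The number of untimed records is not given, so the size of the effect cannot be stated. It is probably small, and the priority is minor.

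**What to change.** In SAP 3.3, replace the single default for ECG, vital signs and glucose (local laboratory and point-of-care) with the following:
- Assign an untimed Day 1 record by its nominal visit or timepoint label. Screening or predose is pretreatment; Minute 5, Hour 6, Hours 0-12 or an hourly post-dose label is on-treatment.
- Do not let an untimed record without a pre-dose label serve as baseline.
- Count unlabelled, untimed glucose and ECG records as on-treatment in abnormality counts.
- Keep the present rule for demography, medical history and genotyping, and for hematology and other chemistry whose only scheduled Day 1 sample is screening.

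The cost is a paragraph of SAP text and a derivation flag. No new data are needed, provided the database carries the labels that the schedule of activities already defines. The downside is that an unlabelled pre-dose value may occasionally be counted as on-treatment. Reporting the number of untimed Day 1 records by domain and arm would show whether the rule mattered.
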